At each visit the severity will be determined based on evaluator-blinded evaluations of the signs and symptoms of acne vulgaris. Evaluations will be scored on a scale of 0-4, with 0 being clear and 4 being severe. Please see the table below for complete definitions.

Score	Grade	Description
0	Clear	Normal, clear skin with no evidence of acne vulgaris
1	Almost clear	Rare non-inflammatory lesions present, with rare non-inflamed papules (papules must be resolving and may be hyperpigmented, though not pink-red)
2	Mild	Some non-inflammatory lesions are present, with few inflammatory lesions (papules/pustules only, no nodulo-cystic lesions)
3	Moderate	Non-inflammatory lesions predominate, with multiple inflammatory lesions evident: several to many comedones and papules/pustules, and there may or may not be one nodulo-cystic lesion
4	Severe	Inflammatory lesions are more apparent, many comedones and papules/pustules, there may or may not be up to 2 nodulo-cystic lesions

Cutaneous safety and tolerability will be evaluated by tabulations of adverse events and Cutaneous Safety and Tolerability Evaluation scores (scaling, erythema, hypo/hyper-pigmentation, itching, burning, and stinging) to be assessed at each study visit. Itching, burning and stinging (Cutaneous tolerability) will be reviewed with the subject at each study visit as an average over the period since the previous visit. Scaling, erythema and hypo/hyper-pigmentation (Cutaneous Safety) will be assessed by the evaluator at each visit. Changes from baseline in all safety laboratory values will be summarized using descriptive statistics by treatment group.

Cutaneous tolerability signs and symptoms that result in the subject requiring concomitant therapy, interruption of treatment, or discontinuation from the study will be reported as an AE. At selected sites, standardized photography of the face will be performed.

Statistical methods:

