8.1 Subject Inclusion Criteria

Subjects meeting all of the following criteria will be eligible for study entry:

1. Male or female at least 9 years of age and older;
2. Written and verbal informed consent must be obtained. Subjects less than age of consent must sign an assent for the study and a parent or a legal guardian must sign the informed consent (if subject reaches age of consent during the study they should be re-consented at the next study visit);
3. Subject must have a score of 3 (moderate) or 4 (severe) on the Evaluator's Global Severity assessment at the screening and baseline visit;
4. Subjects with facial acne inflammatory lesion (papules, pustules, and nodules) count no less than 20 but no more than 40;
5. Subjects with facial acne non-inflammatory lesion (open and closed comedones) count no less than 20 but no more than 100;
6. Subjects with two or fewer facial nodules;
7. Females of childbearing potential¹ and females that are pre-menses must be willing to practice effective contraception for the duration of the study. (Effective contraception is defined as stabilized on oral contraceptive for at least 3 months, IUD, condom with spermicidal, diaphragm with spermicidal, implant, Nuvaring, injection, transdermal patch or abstinence.) Females on birth control pills must have taken the same type pill for at least three months prior to entering the study and must not change type during the study. Those who have used birth control pills in the past must have discontinued usage at least three months prior to the start of the study. Women who use birth control for acne control only should be excluded.
8. Pre-menses females and females of childbearing potential must have a negative urine pregnancy test² at the screening and baseline visits;
9. Subjects must be willing to comply with study instructions and return to the clinic for required visits. Subjects under the age of consent must be accompanied by the parent or legal guardian at the time of assent/consent signing;
10. If a cleanser, moisturizer or sunscreen is needed during the study, Subjects must be willing to use only allowed cleansers, moisturizers, sunscreens, or

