11.4.8 Pregnancy

All female subjects of childbearing potential must use an effective method of birth control during the course of the study, in a manner such that risk of contraceptive failure is minimized. Abstinence is allowed as a birth control method.

Before enrolling a female subject of childbearing potential in this clinical trial, the investigator must review the following information about study participation:

- Informed consent requirements
- Contraceptives in current use

Following review of this information and appropriate subject counseling, the investigator or designee and the subject must sign the informed consent before study enrollment.

During the study, all female subjects of childbearing potential should be instructed to contact the investigator immediately if they suspect they might be pregnant (eg, missed or late menstrual period).

If a subject or investigator suspects that the subject may be pregnant prior to study enrollment, the study drug must be withheld until the results of laboratory pregnancy testing are available. If pregnancy is confirmed, the subject must not receive study drug and must not be enrolled in the study. If pregnancy is suspected while the subject is receiving study treatment, the study drug must immediately be withheld until the result of pregnancy testing is known. If pregnancy is confirmed, the study drug will be permanently discontinued and the subject will be followed until the pregnancy comes to term. A Pregnancy Report form will be submitted to the sponsor, initially and at the end of the pregnancy, which includes the outcome of the pregnancy and any complications occurring during the pregnancy or the delivery.

All confirmed pregnancies must be immediately reported to the medical monitor within 24 hours of the investigator's awareness of the pregnancy. All confirmed pregnancies must be reported via confirmed facsimile/email transmission and must be submitted on a SAE and pregnancy report forms within 24 hours of the investigator's awareness of the pregnancy using the same reporting as procedure for an SAE under Section 11.4.6.

12 Statistics

All statistical processing will be performed using SAS® version 9.3 or later unless otherwise stated. Statistical significance will be based on two-tailed tests of the null hypothesis resulting in p-values of 0.05 or less.

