A similar procedure will be used for the analyses based on proportion of EGSS successes wherein the ANCOVA analysis is replaced with a logistic regression analysis. Specifically, missing 12 week EGSS values from which the dichotomized EGSS is derived will be estimated by (MCMC) which does not rely on the assumption of data missing at random. Additionally, the pattern of missing observations in each treatment group cannot influence the missing value estimation in the other because the imputation is being conducted independently for each treatment group.

The missing 12 week EGSS values will be derived for the analysis using the method of Markov Chain Monte Carlo (MCMC) multiple imputation. Multiple imputation and subsequent analysis will involve 4 principal tasks:

1. Calculate the number of missing values to be estimated by MCMC (nmiss) for 12 week value.
2. Create a data set, one for each treatment group, of subjects with observed values and those needing estimation by MCMC. The missing EGSS values in each data set will be filled in using the MCMC method ‘5 x nmiss’ times to generate ‘5 x nmiss’ data sets. The resulting data sets for each treatment arm will be combined into one complete data set by imputation.

Syntax:

```
proc mi data=datain out=dataout seed=&seed. nimpute=5xnmiss <options>;
  where trtpn=(1, or 2);
  mcmc chain=multiple;
  var baseline week4 week8 week12;
```

run;

3. For each complete data set, the dichotomous success rate (clear or almost clear with a 2-point change from baseline) will be computed. The 12-week estimated global values will be rounded to the nearest integer value prior to evaluating the success rate. Each complete data set will be analyzed with a logistic regression with factors of treatment group and analysis center.
4. The results from these analyses will be combined into a single inference using SAS PROC MIANALYZE.

A total of 2 random seeds will be needed to impute EGSS for the two treatment groups. Those 2 random seeds have been pre-specified by using a random number generator:

- EGSS; IDP-121 Lotion: Seed= 1210644108
- EGSS; IDP-121 Vehicle: Seed= 763715437

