12.1.9 Sensitivity Efficacy Analyses

Sensitivity analyses for absolute change in lesion count

The first sensitivity analysis for absolute change in lesion count use a repeated measures ANCOVA, with treatment, analysis center, and visit (ie, Week 4, Week 8) as independent factors and a covariate of baseline lesion count. In this analysis, data from all post-baseline visits will be included with no imputation for missing data.

The second sensitivity analysis will use the model based multiple imputation method to impute missing data for the absolute change in lesion counts at Week 12. Although the full details will be presented in the Statistical Analysis Plan (SAP), the multiple imputation will involve 4 principal tasks:

1. Calculate the number of missing values (nmiss) for absolute change in lesion count.
2. Missing values will be filled in ‘5 x nmiss’ times to generate ‘5 x nmiss’ complete data sets. The imputation model used will be an ANCOVA with factors of treatment group and analysis center, and a covariate of baseline lesion count (ie, the imputation model will be the same as the analysis model). Appropriate modifications will be made should the analysis be based on a non-parameteric method.
3. Each complete data set will be analyzed with an ANCOVA with factors of treatment group, and analysis center, and a covariate of baseline lesion count.
4. Results from these analyses will be combined into a single inference.

Sensitivity analyses for EGSS

The first sensitivity analysis for the dichotomized EGSS success will use a repeated measures logistic regression model (generalized estimating equations), with dichotomized EGSS success as the dependent variable and treatment, analysis center, and visit (ie, Week 4, Week 8) as independent factors. In this analysis, data from all post-baseline visits will be included with no imputation for missing data.

The second sensitivity analysis will use the model based multiple imputation method to impute missing data for the dichotomized EGSS data. Although the full details will be presented in the SAP, the multiple imputation will involve 4 principal tasks:

1. Calculate the number of missing values (nmiss) for absolute change in lesion count.
2. Missing values will be filled in ‘5 x nmiss’ times to generate ‘5 x nmiss’ complete data sets. The imputation model used logistic regression with factors of treatment group and analysis center (ie, the imputation model will be the same as the analysis model).

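### Missing Week 12 EGSS grades (ordinal, 0 to 4) are imputed from a normal model and rounded before the success cut; this can bias imputed success in either direction, and an ordinal logistic imputation is a cheap improvement

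*Combined protocol and SAP*

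**What the plan says.** The Synopsis defines the score: "Evaluations will be scored on a scale of 0-4, with 0 being clear and 4 being severe". Section 8.1 restricts entry: "Subject must have a score of 3 (moderate) or 4 (severe) on the Evaluator's Global Severity assessment". Section 12.1.1 makes EGSS success at Week 12 one of three co-primary endpoints, and Section 12.1.5 requires all three to be significant.

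For missing Week 12 grades, Section 12.1.8 runs PROC MI separately in each arm, with five times as many imputations as there are missing values. The code has "mcmc chain=multiple" and "var baseline week4 week8 week12"; other options are left open. After imputation, "The 12-week estimated global values will be rounded to the nearest integer value prior to evaluating the success rate", and then "the dichotomous success rate (clear or almost clear with a 2-point change from baseline) will be computed". Each completed data set goes into a logistic regression with treatment and analysis center, and the results are combined with MIANALYZE.

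Section 12.1.9 adds two sensitivity analyses for EGSS. One is a repeated-measures logistic model (GEE) without imputation. The other is a multiple imputation of the dichotomized outcome: "The imputation model used logistic regression with factors of treatment group and analysis center". Further detail on the latter is deferred to the SAP.

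**The concern.** The protocol does not name a multivariate normal model, but that is what the MCMC statement fits. The need to round confirms that the draws are continuous. A five-level grade treated this way is matched on mean and variance only. Success is a lower-tail event, and a normal tail need not equal the observed frequency of grades 0 and 1. More imputations and fixed seeds reduce Monte Carlo noise but do not remove this mismatch.

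EGSS is also the endpoint with the least power in the plan: about 90% in Section 12.8.2, against at least 96% and more than 99% for the two lesion counts. All three must succeed, so an avoidable distortion here bears on the overall result.

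**Working it through.** **Inputs from the documents.** Score 0 to 4; baseline 3 or 4; 400 per arm. Success rates are 23% v 14% (Study 2 of the earlier tretinoin gel) and 13% v 4% (Study 1), both from Section 12.8.2. On the test level, Section 12 says: "Statistical significance will be based on two-tailed tests of the null hypothesis resulting in p-values of 0.05 or less".

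**Assumed, because the documents are silent.** Week 12 grade distributions; 10-20% missing at Week 12; visit correlations of 0.7 (adjacent visits), 0.55 (Week 4 with Week 12) and 0.25 (with baseline); 10% of subjects at baseline grade 4.

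**Step 1: the plan's own power.** With p1 = 0.23, p2 = 0.14 and mean 0.185:
- SE under the null = √(2 × 0.185 × 0.815 / 400) = 0.02746
- SE under the alternative = √((0.23 × 0.77 + 0.14 × 0.86) / 400) = 0.02727
- Power = Φ((0.09 − 1.96 × 0.02746) / 0.02727) = Φ(1.327) = 90.8%

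The stated figure of about 90% is reproduced.

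**Step 2: what the rule does.** From baseline 3, a two-grade reduction means grade 1 or lower. From baseline 4, the Clear or Almost Clear requirement again means grade 1 or lower. After rounding, an imputed subject is a success when the normal draw is below 1.5. Ignoring predictors, imputed success = Φ((1.5 − mean)/SD), while true success = P(0) + P(1).

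**Step 3: three distributions with the same true rate.**

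| Grades 0/1/2/3/4 | Mean | SD | True | Imputed |
|---|---|---|---|---|
| .01/.22/.30/.42/.05 | 2.28 | 0.895 | 23.0% | 19.2% |
| .03/.20/.40/.33/.04 | 2.15 | 0.887 | 23.0% | 23.2% |
| .05/.18/.45/.28/.04 | 2.08 | 0.902 | 23.0% | 26.0% |

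First row: mean = 0.22 + 0.60 + 1.26 + 0.20 = 2.28; variance = 6.00 − 2.28² = 0.8016; Φ((1.5 − 2.28)/0.895) = Φ(−0.871) = 19.2%.

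**Step 4: a grid of 150 assumed shapes per pair of rates, the same shape in both arms.** Bias in percentage points among imputed subjects:

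| Rates | Active: range (median) | Vehicle: range (median) | Both understated | Difference: range |
|---|---|---|---|---|
| 23% v 14% | −6.8 to +6.8 (−0.5) | −4.7 to +8.3 (+1.7) | 32% of shapes | −3.2 to −0.4 |
| 13% v 4% | −4.5 to +8.4 (+1.8) | −1.9 to +8.7 (+3.0) | 13% of shapes | −3.2 to +1.9 |

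Active was understated in 52% of shapes at 23% v 14%. The active bias lay below the vehicle bias in all shapes at 23% v 14% and in 87% at 13% v 4%.

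**Step 5: simulation with predictors.** 400,000 subjects per arm, four visits, normal regression draws given the earlier grades, and shapes allowed to differ by arm. At 23% v 14%, the bias among imputed subjects was −3.8 to +1.9 points (active), −2.5 to +1.9 (vehicle) and −2.6 to +0.5 (difference). At 13% v 4%, the difference bias was −2.0 to +1.2.

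**Step 6: effect on the whole trial.** Overall shift = fraction missing × bias among imputed subjects. At 20% missing, 0.2 × (−2.6) ≈ −0.5 and 0.2 × 0.5 = +0.1 points on the 9-point difference. One of the less favorable cases has active −0.7 and vehicle +1.8 at 20% missing. The rates become 0.23 − 0.2 × 0.007 = 0.2286 and 0.14 + 0.2 × 0.018 = 0.1436, and power is 87.2%. If both arms are overstated by 1.7 points, the difference is unchanged and power is 90.4%. The overall range is roughly 87-91%.

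**Step 7: the alternative.** In a simulation with data missing at random, ordinal logistic imputation came within about 0.5 points of the true rate among imputed subjects. Normal draws with rounding missed by up to about 2.4 points.

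**The case against.** A reader might infer that the method understates success, more so in the active arm, and so introduces a systematic error against the product. The documents do not support that. The sign depends on the Week 12 grade distribution in each arm, and Section 12.8.2 gives success rates only. Overstatement is as easy to produce, especially in the vehicle arm and at the Study 1 rates. The tendency toward a smaller arm difference is clearest when both arms share a grade shape, and it can reverse when they do not.

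Three other arguments for the plan deserve weight:
- **Small effect, often conservative.** This stands as to size. It does not make the method safe, because a conservative direction cannot be guaranteed either.
- **The two-valued baseline is not a fault.** This stands. Baseline is an eligibility measure, should be observed for everyone, and a two-valued predictor is acceptable in a normal regression. Draws outside 0 to 4 are also harmless: those below 0 count as success and those above 4 as failure.
- **Sensitivity analyses without a normal model or rounding exist.** This stands in part. The GEE analysis uses the observed interim outcomes but does not impute. The logistic imputation lists only treatment and analysis center, so if it disagreed with the primary analysis, one could not tell whether rounding or the missing EGSS predictors was the cause. The SAP might add predictors, but Section 12.1.9 describes the imputation model as identical to the analysis model.

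**Conclusion.** The concern holds as a calibration weakness of unknown sign. A co-primary ordinal endpoint is imputed by a method whose success rate can be several points too high or too low among imputed subjects. The likely effect on the trial is small: about −0.5 to +0.1 points on a 9-point difference at an assumed 10-20% missing, with power of roughly 87-91% instead of 90.8%.

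These ranges describe the shapes that were tried and are not bounds. The closed form without predictors, for example, gives up to 0.2 × (−3.2) = −0.64 points. Grade distributions, correlations and missing fraction are all assumptions. The case for changing the plan rests on low cost, the co-primary role and the lack of any planned analysis that combines a categorical imputation model with the interim grades. It is a cheap improvement.

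**What to change.** In Section 12.1.8 and the SAP, replace the MCMC step for EGSS with an ordinal logistic imputation by arm, using PROC MI with FCS LOGISTIC, or MONOTONE LOGISTIC where the missing pattern is monotone. Use baseline, Week 4 and Week 8 EGSS as predictors, and add analysis center where cell sizes allow, since it is in the analysis model. Derive success directly from the imputed category and delete the rounding step. Keep the by-arm structure, the number of imputations and the pre-specified seeds.

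The cost is a change of imputation statement and some convergence checking, because grades 0 and 4 may be sparse within an arm. Pre-specify the fallback: collapse rare grades (for example 0 with 1, which leaves the success cut intact), or impute success itself with a binary logistic model on the same predictors. Section 12 has the SAP finalized before unblinding, so the change should be made by then.

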9.2 Randomization and Blinding

The study drugs will be packaged and labeled identically, and the study drug kits will be numbered sequentially and dispensed randomly to the subjects entering the study within each investigational center. Study drug supplies will be distributed to the investigational centers to maintain the randomization ratio within each investigational center.

As a double-blinded study, the investigators, the site staff, the sponsor, and the clinical monitors will not be aware of the treatment assigned to the individual study subjects. Delegated staff members at each investigational center will dispense the study drugs and will collect all used and unused study drug tubes as scheduled.

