12.1.5 Statistical Hypothesis Testing and Control of Multiplicity

Statistical hypothesis testing for lesion count analyses will use the statistical model introduced in Section 12.1.3 and employs the methods of Section regarding missing values. The analysis of the dichotomized Evaluator's Global Severity Score will be based on the logistic regression test stratified by analysis center and employs the methods of Section 12.1.7 regarding missing values.

The overall Type I error will be controlled by requiring the co-primary efficacy endpoints of each group to be statistically significant. Specifically, failure of any one of the primary efficacy endpoints will invalidate the statistical significance of the secondary efficacy endpoints.

The following stepwise process will be conducted for testing the secondary efficacy endpoints in order to control for multiplicity. These tests will be performed for only the ITT population. The testing process will terminate whenever a statistical test for a step is not significant. All subsequent tests for the remaining steps will be considered not significant. The order of testing is:

Step Number	Secondary Endpoint
1	Percent change in non-inflammatory lesion count from baseline to Week 12
2	Percent change in inflammatory lesion count from baseline to Week 12

The following stepwise process will be conducted for testing the supportive efficacy endpoints in order to control for multiplicity. These tests will be performed for only the ITT population. In order to control for multiplicity failure of any one of the secondary efficacy endpoints will invalidate the statistical significance of the supportive efficacy endpoints. The testing process will terminate whenever a statistical test for a step is not significant. All subsequent tests for the remaining steps will be considered not significant. The order of testing is:

Step Number	Supportive Endpoint
1	Percent change in non-inflammatory lesion count from baseline to Week 8
2	Percent change in inflammatory lesion count from baseline to Week 8
3	Percent change in non-inflammatory lesion count from baseline to Week 4
4	Percent change in inflammatory lesion count from baseline to Week 4
5	Proportion of subjects who have at least a 2 grade reduction at Week 12 from

	baseline in the Evaluator's Global Severity Score
6	Proportion of subjects who have at least a 2 grade reduction at Week 8 from baseline in the Evaluator's Global Severity Score

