3. Each complete data set will be analyzed with a logistic regression a factors of treatment group and analysis center.
4. Results from these analyses will be combined into a single inference.

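### The EGSS co-primary model and both EGSS sensitivity models leave out baseline EGSS grade; adding it is a cheap, minor gain of about 0 to 1 point of power

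*Combined protocol and SAP*

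**What the plan says.** All references are to the current protocol (Amendment 3).

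- **Primary EGSS test.** Section 12.1.5 says the analysis "will be based on the logistic regression test stratified by analysis center". Section 12.1.8 gives the model fitted to each imputed data set: "Each complete data set will be analyzed with a logistic regression with factors of treatment group and analysis center".
- **First sensitivity analysis (Section 12.1.9).** A GEE "with dichotomized EGSS success as the dependent variable and treatment, analysis center, and visit" as factors.
- **Second sensitivity analysis (Section 12.1.9).** For imputation: "The imputation model used logistic regression with factors of treatment group and analysis center". For analysis: "Each complete data set will be analyzed with a logistic regression a factors of treatment group and analysis center".
- **Where baseline EGSS does appear.** The PROC MI syntax for the primary EGSS imputation in Section 12.1.8 has "var baseline week4 week8 week12". Section 12.1.10 lists baseline global severity as a descriptive subgroup.
- **Lesion counts, by contrast.** The ANCOVA in Section 12.1.4 and both lesion-count sensitivity analyses in Section 12.1.9, including the imputation model, carry the baseline count as a covariate.
- **Eligibility and randomization.** Section 8.1 admits grades 3 and 4 only. Allocation is 1:1, with kits "dispensed randomly to the subjects entering the study within each investigational center" (Section 9.2). No stratification by severity is described.

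**The concern.** Success requires Clear or Almost Clear and at least a two-grade reduction. As everyone enters at 3 or 4, this reduces to a Week 12 score of 0 or 1: a fall of two grades for a grade-3 subject and three for a grade-4 subject. The scale is static, so how strongly baseline grade predicts success is an empirical matter, but an association is very likely. Leaving a prognostic baseline value out of a logistic model costs some power.

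All three co-primaries must succeed, and Section 12.8.2 gives EGSS the lowest power: about 90%, against at least 96% and above 99% for the lesion counts. A small gain is worth most there. Naming the covariate in advance also settles how a chance imbalance in severity will be handled.

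A second issue concerns the model-based imputation in Section 12.1.9. Within an arm and center it gives a grade-4 dropout the same success probability as a grade-3 dropout. It is meant to check the primary imputation, yet it drops a predictor which that imputation uses.

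**Working it through.** **Inputs from the documents.** Two-sided 0.05 (Section 12); 23% versus 14% and 400 per arm (Section 12.8.2); 1:1 allocation (Section 9.1).

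**Assumed inputs.** The share of subjects at grade 4 (5% to 30%) and the odds ratio (OR) of success for grade 4 against grade 3 (0.2 to 0.67). Neither is in the documents.

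**1. The plan's own power.**
- Pooled two-proportion test: mean rate 0.185; null SE = √(2 × 0.185 × 0.815 / 400) = 0.02746; alternative SE = √((0.23 × 0.77 + 0.14 × 0.86) / 400) = 0.02727. z = (0.09 − 1.96 × 0.02746) / 0.02727 = 1.327, so power is 90.8%. This agrees with the stated figure of about 90%.
- Lesion counts: 3.0 with SD 11.3 gives 96.4%; 7.9 with SD 24.7 gives 99.5%. Both agree with the plan, and EGSS is the lowest of the three.

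**2. Unadjusted logistic Wald test.** Log OR = ln(0.23/0.77) − ln(0.14/0.86) = 0.607 (OR 1.835). Information = 400 × v₁v₀/(v₁ + v₀), with v₁ = 0.1771 and v₀ = 0.1204, which is 28.67. z = 0.607 × √28.67 = 3.250; power = Φ(3.250 − 1.960) = 90.15%.

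**3. Adjusted test.** Solve for the intercept and a common conditional treatment effect so that the marginal rates stay at 14% and 23%; sum the information over the two grades; power = Φ(β√information − 1.960).

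Worked case, 20% at grade 4, OR 0.33: success for grade 3/grade 4 is 26.1%/10.5% on active and 16.0%/5.9% on vehicle. Information is 25.37 + 2.79 = 28.16, β = 0.618 (OR 1.855), z = 3.279, power 90.64%.

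| Grade-4 share | OR | Adjusted power | Gain (points) |
|---|---|---|---|
| any | 1 | 90.15% | 0 |
| 5% | 0.67 | 90.17% | 0.02 |
| 10% | 0.67 | 90.20% | 0.05 |
| 10% | 0.33 | 90.40% | 0.25 |
| 20% | 0.33 | 90.64% | 0.50 |
| 30% | 0.33 | 90.88% | 0.73 |
| 30% | 0.2 | 91.39% | 1.24 |

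Relative efficiency runs from 1.001 to 1.047, and the conditional odds ratio from 1.836 to 1.887. Outside this grid the gain grows: about 1.4 points at 40%/0.25 and 1.6 at 50%/0.25.

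**4. Simulation.** With 40 centers of 10 per arm, an assumed center SD of 0.5 on the logit scale, center in both models and 3,000 trials per setting, the gains were −0.07 (Monte Carlo SE 0.14) at 10%/0.67, 0.93 (0.22) at 20%/0.33, 0.50 (0.26) at 30%/0.33 and 1.27 (0.29) at 30%/0.2. A separate run without centers, 20,000 trials per setting, gave 0.7 at 20%/0.25 and 0.8 at 30%/0.33.

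**5. At the sponsor's expected 95% power.** This needs about 24% versus 14% (95.1% pooled). The gain there is 0.02 to about 0.9 points.

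**6. Chance imbalance.** The SD of the between-arm difference in grade-4 share is √(2π(1 − π)/400), with π the grade-4 share: 1.5 points at 5% and 3.2 at 30%. A two-SD imbalance moves the treatment difference by 0.2 to 1.2 points, against an SE of 2.7 and a planned difference of 9.

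**The case against.** The best case against is that this is a preference and not a defect. The planned test is valid, its type I error is sound, and the gain is small. That is true, and it is why the point is minor.

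The size rests on two assumed inputs. Entry limits on lesion counts and nodules narrow severity in both grades and could weaken the association. The 0-to-1 range depends on the grid chosen; larger grade-4 shares give more. The smaller simulation is noisy (its ordering at OR 0.33 reverses the analytic one), and no calculation includes missing data or the rounding of imputed scores. These limits stand, and the figures should be read as assumption-driven.

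The imputation argument also needs a limit. If dropout is unrelated to grade, ignoring grade does not move the expected arm rates: 0.8 × 26.1 + 0.2 × 10.5 = 23.0% and 0.8 × 16.0 + 0.2 × 5.9 = 14.0%. Bias in the treatment contrast needs dropout to depend on grade, and differently by arm. The documents say nothing on that.

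Finally, Section 12.1.9 leaves full details of the model-based imputation to a separate SAP, which was not supplied and might add the term. But the protocol already names the covariates of each EGSS model, and baseline EGSS is not among them.

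**Conclusion.** The concern holds, as a minor point of efficiency. No EGSS analysis model in the current protocol adjusts for baseline grade, nor does the model-based EGSS imputation, while the lesion-count counterparts adjust for baseline count and the primary EGSS imputation uses baseline EGSS. The protocol gives no reason for leaving baseline grade out of the EGSS analysis models.

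On the assumed range the benefit is roughly 0 to 1 point of power on the lowest-powered co-primary, and nothing if grade is not prognostic. Chance imbalance is a lesser reason. The sensitivity imputation is better for including grade, but no bias in it has been shown.

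**What to change.** Before unblinding, specify logistic regression with treatment, analysis center and baseline EGSS (3 versus 4) for the primary EGSS analysis in Sections 12.1.5 and 12.1.8, and for both the imputation and analysis steps of the second sensitivity analysis in Section 12.1.9. Add the same term to the GEE. State that the odds ratio is conditional on baseline grade and center, and report a standardized (marginal) risk difference from the same model.

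The cost is one covariate that is already collected; design, sample size and conduct do not change. The odds ratio moves slightly, from 1.835 to between 1.836 and 1.887 in the scenarios above. The risk difference and its variance have to be computed in each imputed data set and pooled, which is modest extra programming.
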